5.4.1.2.5. INCB059872 Dose Modifications

Table 14 describes INCB059872 dose reductions that may occur due to any related AEs. Dose reductions should occur in a step-wise fashion from the initial starting dose of the cohort, and a maximum of 2 dose reductions of INCB059872 are allowed for the management of an AE, regardless of the initial starting dose. If an AE recurs/does not return to baseline after the second dose reduction of INCB059872, then the subject must permanently discontinue INCB059872. The lowest permissible dose of INCB059872 is 1 mg QoD. If a subject does not tolerate 1 mg QoD, alternative dose schedules may be evaluated.

Table 14: INCB059872 Dose Reductions

Dose Level
3 mgQoD
2 mg QoD/1 mg QD ^a
1 mgQoD

Table 15: Dose Modification Guidelines for Drug-Related Adverse Events (Treatment Group A)

Toxicity	Grade	Hold Treatment (Y/N)	Timing for Treatment Restart	Dose/Schedule for Treatment Restart			Discontinue Subject (After Medical Monitor Consultation)
				Azacitidine	Epacadostat	Pembrolizumab	
Hematologic toxicity	1, 2	No	N/A	N/A	N/A	N/A	N/A
	3	Hold azacitidine	Toxicity resolves to Grade 1 or baseline.	Restart at same dose if the toxicity resolves within 7 days.	N/A	N/A	N/A
	4	Yes	Toxicity resolves to Grade 1 or baseline.	Restart at 1 dose level lower if the toxicity resolves within 7 days.	Reduce dose by 1 dose level.	Restart at same dose for the following events: Grade 4 neutropenia lasting 7 days, Grade 4 lymphopenia or leukopenia. For all other Grade 4 hematologic toxicities, treatment with pembrolizumab may not be restarted.	Toxicity does not resolve within 6 weeks of last infusion. Permanent discontinuation should be considered for any severe or life-threatening event.
Nonhematologic toxicity Note: Exception to be treated to similar Grade 1 toxicity: - Grade 2 alopecia - Grade 2 fatigue - Grade 3 rash in the absence of desquamation, without mucosal involvement, not requiring systemic steroids, and that resolves to Grade 1 within 14 days. For additional information regarding AE with potential immune etiology, see Section 5.4.1.3.	1	No	N/A	N/A	N/A	N/A	N/A
	2	Consider holding for persistent symptoms	Toxicity resolves to Grade 1 or baseline.	Restart at same dose.	Restart at same dose.	Restart at same dose.	Toxicity does not resolve within 6 weeks of last infusion.

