	3	Yes*	Toxicity resolves to Grade 1 or baseline.	Restart at same dose.	Restart at 1 dose level lower.	Restart at same dose.*	Toxicity does not resolve within 6 weeks of last infusion. Permanent discontinuation should be considered for any severe or life-threatening event.
	4	Yes	Toxicity resolves to Grade 1 or baseline.	Restart at 1 dose level lower.	Restart at 1 dose level lower.	Restart only permitted only as noted. ^b For all other Grade 4 nonhematologic toxicities, treatment with pembrolizumab may not be restarted.	Toxicity does not resolve within 6 weeks of last infusion. Permanent discontinuation should be considered for any severe or life-threatening event.

Note: Subjects who experience a recurrence of the same severe or life-threatening AE at the same grade or greater treatment should be discontinued from study treatment.

* The following exceptions for asymptomatic amylase or lipase do not require a dose delay: Grade 3 amylase or lipase abnormalities that are not associated with symptoms or clinical manifestations of pancreatitis. It is recommended to consult with the medical monitor for Grade 3 amylase or lipase abnormalities.

^b Isolated Grade 4 lipase or amylase abnormalities not associated with symptoms or clinical manifestations of pancreatitis. Medical monitor should be consulted for any Grade 4 amylase or lipase abnormality.

Table 16: Dose Modification Guidelines for Drug-Related Adverse Events (Treatment Group B)

Toxicity	Grade	Hold Treatment (Y/N)	Timing for Treatment Restat1	Dose/Schedule for Treatment Restat1			Discontinue Subject (After Medical Monitor Consultation)
				INCB057643	Epacadostat	Pembrolizumab	
Hematologic toxicity	1, 2	No	N/A	N/A	N/A	N/A	N/A
	3	Hold INCB057643	Toxicity resolves to Grade 1 or baseline.	Restart at 1 dose level lower if the toxicity resolves within 7 days.	N/A	N/A	N/A
	4	Yes	Toxicity resolves to Grade 1 or baseline.	Restart at 1 dose level lower if the toxicity resolves within 7 days. If already at lowest dose, discontinue. If evidence of bleeding, patient should pennisantly discontinue.	Reduce dose by 1 dose level. If already at lowest dose, discontinue	Restart at same dose.	Toxicity does not resolve within 6 weeks of last infhsion. Permanent discontinuation should be considered for any severe or life-threatening event.

Table 16: Dose Modification Guidelines for Drug-Related Adverse Events (Treatment Group B) (Continued)

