5.4.1.3. Procedures for Subjects Exhibiting Immune-Related Adverse Events

This section is meant to apply to suspected irAEs from epacadostat, pembrolizumab, or the combination.

Immune-related AEs may be defined as an AE of unknown etiology, associated with drug exposure and consistent with an immune phenomenon. Immune-related AEs may be predicted based on the nature of the pembrolizumab or epacadostat compounds, their mechanism of action, and reported experience with immunotherapies that have a similar mechanism of action. Special attention should be paid to AEs that may be suggestive of potential irAEs. An irAE can occur shortly after the first dose or several months after the last dose of treatment.

If an irAE is suspected, efforts should be made to rule out neoplastic, infectious, metabolic, toxin or other etiologic causes before labeling an AE as an irAE. Subjects who develop a Grade 2 irAE should be discussed immediately with the sponsor.

General recommendations to managing irAEs not detailed elsewhere in the Protocol are detailed in Table 18. Recommendations for management of specific immune-mediated AEs such as pneumonitis (Section 5.4.1.3.1), enterocolitis (Section 5.4.1.3.2), hepatitis (Section 5.4.1.3.3), dermatitis (Section 5.4.1.3.4), neuropathies (Section 5.4.1.3.5), endocrinopathies (Section 5.4.1.3.6), myocarditis (Section 5.4.1.3.7), and other immune-mediated AEs (Section 5.4.1.3.8) are detailed in the sections below.

Table 18: General Approach to Handling Immune-Related Adverse Events

irAE	Withhold/Discontinue Pembrolizumab and Epacadostat	Guidance for Restarting Study Treatment	Supportive Care
Grade 1	No action.	Not applicable.	Provide symptomatic treatment.
Grade 2	May withhold pembrolizumab and epacadostat per investigator's discretion.	May return to treatment if improves to Grade 1 or resolves within 6 weeks. If AE resolves within 4 weeks, subject may restart at the same dose and schedule for both pembrolizumab and epacadostat. For an AE that does not resolve within 4 weeks, epacadostat should be reduced 1 dose level, but pembrolizumab may be restarted at the same dose and schedule. If AE does not resolve within 6 weeks, study treatment with both study drugs should be discontinued or discussed with medical monitor.	Consider systemic corticosteroids in addition to appropriate symptomatic treatment.

Table 18: General Approach to Handling Immune-Related Adverse Events
 (Continued)

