5.4.1.3.4. Procedures for Immune-Mediated Dermatitis

Monitor subjects for signs and symptoms of dermatitis such as rash and pruritus. Unless an alternate etiology has been identified, signs or symptoms of dermatitis should be considered immune-mediated. Recommendations for management of dermatitis are shown in [Table 22](#).

Table 22: Recommended Approach for Handling Dermatitis

irAE	Withhold/Discontinue Pembrolizumab and Epacadostat	Guidance for Restarting Study Treatment	Supportive Care
Grade 1	No action.	Not applicable.	For mild to moderate dermatitis, such as localized rash and pruritus, treat symptomatically. Administer topical or systemic corticosteroids if there is no improvement of symptoms within 1 week.
Grade 2	No action.	Not applicable.	For mild to moderate dermatitis, such as localized rash and pruritus, treat symptomatically. Administer topical or systemic corticosteroids if there is no improvement of symptoms within 1 week.
Grades 3 and 4	Withhold epacadostat and pembrolizumab in subjects with moderate to severe signs and symptoms of rash. Permanently discontinue epacadostat and pembrolizumab in subjects with Stevens-Johnson syndrome, toxic epidermal necrolysis, or rash complicated by full thickness dermal ulceration or by necrotic, bullous, or hemorrhagic manifestations.	If AE resolves to baseline within 4 weeks, subject may restart at the same dose and schedule for both pembrolizumab and epacadostat. For an AE that does not resolve within 4 weeks, epacadostat should be reduced 1 dose level, but pembrolizumab may be restarted at the same dose and schedule. If AE does not resolve within 6 weeks, study treatment with both study drugs should be discontinued or discussed with medical monitor.	Administer systemic corticosteroids at a dose of 1 to 2 mg/kg per day of prednisone or equivalent. When dermatitis is controlled, corticosteroid tapering should occur over a period of at least 1 month.

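### Table 22's combined Grade 3 and 4 row lets both immunotherapies restart at the same dose after some Grade 4 rashes, against Table 15 and the other seven irAE tables

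*Protocol*

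**What the plan says.** **Rash.** Section 5.4.1.3 opens with its scope: "This section is meant to apply to suspected irAEs from epacadostat, pembrolizumab, or the combination". Section 5.4.1.3.4 then sets a default: "Unless an alternate etiology has been identified, signs or symptoms of dermatitis should be considered immune-mediated". Table 22 gives Grades 3 and 4 one row. Both drugs are withheld for moderate to severe rash. They are stopped for good in Stevens-Johnson syndrome, toxic epidermal necrolysis, or rash with full-thickness ulceration or necrotic, bullous or hemorrhagic features. For the rest: "If AE resolves to baseline within 4 weeks, subject may restart at the same dose and schedule for both pembrolizumab and epacadostat". The medical monitor first appears in the row at 6 weeks without resolution.

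Table 15 covers drug-related adverse events in Treatment Group A generally. After a Grade 4 nonhematologic event, epacadostat resumes one level lower. Isolated asymptomatic lipase or amylase elevation is the only case in which pembrolizumab may resume: "For all other Grade 4 nonhematologic toxicities, treatment with pembrolizumab may not be restarted". Its link to the immune section is a pointer: "For additional information regarding AE with potential immune etiology, see Section 5.4.1.3".

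**Endocrinopathy.** Table 24 (Section 5.4.1.3.6) has separate rows for Grades 2, 3 and 4, each with its own steroid and restart text.

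**Other irAEs.** "General recommendations to managing irAEs not detailed elsewhere in the Protocol are detailed in Table 18". At Grade 3, Table 18 allows either withholding or stopping, with any restart to be discussed with the medical monitor. Section 5.4.1.3.8 asks for permanent discontinuation of both drugs for 'severe' immune-mediated reactions and does not define the word.

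**The concern.** Restart rules should become more cautious as grade rises, and two rules that reach the same subject should agree. Table 22 fails on both counts at Grade 4. A site that follows it may resume both drugs at the dose that preceded a Grade 4 rash, while a site that follows Table 15 may not resume pembrolizumab at all. Table 24 also runs the wrong way, from Grade 2 to Grade 3.

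Enrollment has stopped (Appendix E, Amendment 4), but the rules still govern care. Subjects may receive up to 35 pembrolizumab administrations, and Section 6.2 allows up to 17 further cycles after progression. What is at stake is the safety of those subjects and consistent handling between sites. The only data touched are the interruption and discontinuation counts in SAP Section 8.2.5.

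**Working it through.** No arithmetic applies; the check sets the texts side by side.

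**1. Do both rules reach the same subject?** Yes. Rash is presumed immune-mediated, so Table 22 applies by default. A drug-related rash is also a nonhematologic toxicity under Table 15. Table 15's pointer offers further information and states no order of precedence.

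**2. Grade 4 rule in each table**

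| Protocol table | Grade 4 instruction |
|---|---|
| 15 (all drug-related AEs, Group A) | Pembrolizumab not restarted (lipase/amylase exception only); epacadostat one level lower |
| 18, 19, 20, 21, 23, 24 (irAEs) | Stop both drugs; exceptions only with medical monitor approval |
| 25 (myocarditis) | Stop both drugs permanently |
| 22 (dermatitis), outside its stop list | Both drugs may restart at the same dose if back to baseline within 4 weeks |

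Seven of the eight irAE tables (18-25) stop both drugs at Grade 4. Table 22 is the only one that does not, and it departs in the less protective direction.

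**3. Do other sections catch the restart?** Three rules turn on a delay of more than 14 days. Section 5.2.2.1 requires medical monitor discussion of a longer pembrolizumab delay. Section 5.4.1.2 asks the investigator to contact the sponsor before restarting. Section 5.4.4 makes the stop permanent unless the sponsor approves a longer delay.

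| Time for rash to return to baseline | Table 22 | 14-day rules triggered? |
|---|---|---|
| Up to 14 days | Same dose, both drugs | No |
| Over 14 days, up to 4 weeks | Same dose, both drugs | Yes, if dosing is delayed that long |
| Over 4 weeks, up to 6 weeks | Epacadostat one level lower, pembrolizumab same dose | Yes |
| Over 6 weeks | Stop, or discuss with monitor | Yes |

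The first row is the gap. The control left there is Section 5.4.1.3's instruction to discuss irAEs with the sponsor immediately. The extracted text says Grade 2; I assume a 'Grade 2 or higher' sign was lost, which is the reading more favorable to the plan. Even then, the two people talking have two conflicting restart rules in front of them.

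**4. Table 24**

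| | Grade 2 | Grade 3 | Grade 4 |
|---|---|---|---|
| Hold | May withhold | Withhold or discontinue | Discontinue |
| Steroids 1-2 mg/kg | 'Initiate' | 'Consider' | 'Consider' |
| Same-dose restart within 4 weeks | Must resolve | Resolved or 'controlled' | None, unless monitor approves |
| Unresolved at 6 weeks | Discontinue | Discontinue or discuss with monitor | Not applicable |

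The hold row is in the right order. The steroid row is firmer at Grade 2 than at Grades 3 and 4, and the two restart rows are stricter at Grade 2 than at Grade 3. Because Grade 2 is only an optional hold, its restart text matters only for subjects whose drug was actually withheld.

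**5. 'Severe' in Section 5.4.1.3.8.** The Section 8.1.2 scale describes Grade 3 as severe or medically significant, and Section 8.2 attaches the word to Grades 3 and 4. If 'severe' includes Grade 3, a restart allowed by Table 18 breaches Section 5.4.1.3.8. If it means Grade 4 only, the two agree.

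**The case against.** The best defense is that these tables do not act alone. Section 5.4.1.2 calls the dose-reduction rules in Tables 15-17 guidelines, and Tables 19-25 are titled as recommended approaches. Any hold beyond 14 days already involves the sponsor or medical monitor, and irAEs are to be discussed with the sponsor at onset. Table 22's stop list removes the gravest rashes. Section 1.7.2 reports no treatment-related Grade 4 events with the pembrolizumab and epacadostat doublet. All of this stands and keeps the point small. It does not close the gap for a rash that clears within 14 days.

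Three stronger readings are tempting, and the documents do not support them.

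- **That uncomplicated Grade 3 rash is under two opposed orders, and Table 22 should adopt Table 15's exception.** Table 15 does treat like Grade 1 a "Grade 3 rash in the absence of desquamation, without mucosal involvement, not requiring systemic steroids, and that resolves to Grade 1 within 14 days", whereas Table 22 says: "Administer systemic corticosteroids at a dose of 1 to 2 mg/kg per day of prednisone or equivalent". But Section 5.4.1.3 is written for suspected irAEs and Table 15 points to it, so Table 22 most naturally governs; what is missing is mainly a precedence sentence. Resolution within 14 days also cannot be known when deciding whether to hold, so the exception would not work as a holding rule.
- **That Section 5.4.1.3.8 flatly contradicts Table 18.** This needs 'severe' to mean Grade 3. The Section 8.1.2 scale is for events CTCAE does not classify, and the Section 8.2 phrase concerns laboratory abnormalities. The word is undefined; the contradiction is conditional. A permanent stop satisfies both texts.
- **That Table 24's Grade 2 steroid instruction is too strong.** The table covers hypophysitis and adrenal crisis, so the order could equally be restored by strengthening Grades 3 and 4. That is a clinical choice.

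The missing monitor option at 6 weeks is not unique to Table 24: Table 21 Grade 2 lacks it too. There, however, Grades 3 and 4 stop both drugs, so nothing is inverted.

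**Conclusion.** The point holds for Grade 4 rash. Table 22 permits a same-dose restart of both drugs that Table 15 forbids for pembrolizumab and reduces for epacadostat, and that no other irAE table offers without an exception. Table 24's inversion is plain on the page and secondary. The undefined 'severe' is an ambiguity that becomes a conflict on one reading.

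The size is small: a minor safety-consistency correction for subjects still on treatment or re-treatment. The documents give no count of affected subjects, and the Grade 4 case should be rare. No effect on ORR, PFS or DOR follows, and a reader should not infer one. Nor do the documents support saying that restarts go unsupervised.

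The conclusion assumes that a Grade 4 rash outside the stop list can occur and return to baseline within 4 weeks. The part left outside the delay rules assumes resolution within 14 days.

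**What to change.** 1. **Table 22.** Split the row. Grade 3 keeps its present text. Grade 4 takes the wording already used at Grade 4 in Table 24: discontinue both drugs, with exceptions only on medical monitor approval. Keep the permanent-stop list in force at both grades, so that the exception clause does not loosen it.
2. **Table 15.** State that Section 5.4.1.3 takes precedence for suspected irAEs. Make this change together with the first: alone, it would let Table 22's present Grade 4 restart override Table 15's bar.
3. **Table 24, Grade 2.** Use the Grade 3 restart wording, so that a controlled event qualifies and the 6-week stop carries the medical monitor option. Have the sponsor's clinical team set the steroid wording so that Grade 2 is not firmer than Grades 3 and 4, in whichever direction they judge right.
4. **Section 5.4.1.3.8.** State which grade or grades 'severe' means, and check the result against Table 18.

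The cost is a protocol clarification letter or a short amendment. No assessments are added and no planned analysis changes.

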5.4.1.3.5. Procedures for Immune-Mediated Neuropathies

Subjects should be monitored for symptoms of motor or sensory neuropathy such as unilateral or bilateral weakness, sensory alterations, or paresthesia. Recommendations for management of neuropathies are shown in [Table 23](#).

Table 23: Recommended Approach for Handling Neuropathies

irAE	Withhold/Discontinue Pembrolizumab and Epcadostat	Guidance for Restarting Study Treatment	Supportive Care
Grade 1	No action.	Not applicable.	Provide symptomatic treatment.
Grade 2	May withhold pembrolizumab and epacadostat.	If AE resolves to Grade 1 or baseline within 4 weeks, subject may restart at the same dose and schedule for both pembrolizumab and epacadostat. For an AE that does not resolve within 4 weeks, epacadostat should be reduced 1 dose level but pembrolizumab may be restarted at the same dose and schedule. If AE does not resolve within 6 weeks, study treatment with both study drugs should be discontinued or discussed with medical monitor.	Consider systemic corticosteroids in addition to appropriate symptomatic treatment.
Grades 3 and 4	Discontinue pembrolizumab and epacadostat.	Not applicable. Any exceptions require medical monitor approval.	Consider initiation of systemic corticosteroids at a dose of 1 to 2 mg/kg per day prednisone or equivalent for severe neuropathies. Institute medical intervention as appropriate for management of severe neuropathy.

5.4.1.3.6. Procedures for Immune-Mediated Endocrinopathies

Subjects should be monitored for clinical signs and symptoms of hypophysitis, adrenal insufficiency (including adrenal crisis), and hyper- or hypothyroidism. Subjects may have fatigue, headache, mental status changes, abdominal pain, unusual bowel habits, and hypotension or have nonspecific symptoms that may resemble other causes such as brain metastasis or underlying disease. Unless an alternate etiology has been identified, signs or symptoms of endocrinopathies should be considered immune-mediated.

Thyroid function tests and clinical chemistries should be monitored at the start of treatment, before each dose and as clinically indicated based on symptoms. In a limited number of subjects, hypophysitis was diagnosed by imaging studies through enlargement of the pituitary gland. Recommendations for management of endocrinopathies are shown in [Table 24](#).

Table 24: Recommended Approach for Handling Endocrinopathies

irAE	Withhold/Discontinue Pembrolizumab and Epacadostat	Guidance for Restarting Study Treatment	Supportive Care
Grade 1	No action.	Not applicable.	Provide symptomatic treatment.
Grade 2	May withhold pembrolizumab and epacadostat.	If AE resolves within 4 weeks, subject may restart at the same dose and schedule for both pembrolizumab and epacadostat. For an AE that does not resolve within 4 weeks, epacadostat should be reduced 1 dose level, but pembrolizumab may be restarted at the same dose and schedule. If AE does not resolve within 6 weeks, study treatment with both study drugs should be discontinued.	Initiate systemic corticosteroids treatment at a dose of 1 to 2 mg/kg per day of prednisone or equivalent, and initiate appropriate hormone replacement therapy.
Grade 3	Withhold or discontinue both pembrolizumab and epacadostat.	If AE resolves or is controlled within 4 weeks, subject may restart at the same dose and schedule for both pembrolizumab and epacadostat. For an AE that does not resolve within 4 weeks, epacadostat should be reduced 1 dose level, but pembrolizumab may be restarted at the same dose and schedule. If AE does not resolve within 6 weeks, study treatment with both study drugs should be discontinued or discussed with medical monitor	Consider initiating systemic corticosteroids treatment at a dose of 1 to 2 mg/kg per day of prednisone or equivalent, and initiate appropriate hormone replacement therapy.
Grade 4	Discontinue both pembrolizumab and epacadostat.	Not applicable. Any exceptions require medical monitor approval.	Consider initiation of systemic corticosteroids at a dose of 1 to 2 mg/kg per day of prednisone or equivalent, and initiate appropriate hormone replacement therapy.

5.4.1.3.7. Procedures for Immune-Mediated Myocarditis

Subjects should be monitored for clinical signs and symptoms of myocarditis. Subjects may have fatigue, chest pain, decreased exercise capacity, increased jugular venous pressure, hepatomegaly, dyspnea, orthopnea, pulmonary rales, pulmonary edema, heart failure, or cardiogenic shock. Unless an alternate etiology has been identified, signs or symptoms of

myocarditis should be considered immune-mediated. Recommendations for management of myocarditis are shown in [Table 25](#).

Table 25: Recommended Approach for Handling Myocarditis

irAE	Withhold/Discontinue Pembrolizumab and Epacadostat	Guidance for Restarting Study Treatment	Supportive Care
Grade 1 and 2	Withhold pembrolizumab and epacadostat.	Withhold both epacadostat and pembrolizumab until Grade 0. May restart at same dose level.	Based on severity of AE administer corticosteroids.
Grade 3 and 4	Withhold pembrolizumab and epacadostat.	Permanently discontinue.	

